Due to the impact of the COVID-19 pandemic and associated restrictions and worry, it has been increasingly challenging to provide informed consent *in person* with legally authorized representatives. Hospital restrictions combined with a general reluctance of LAR's desire to come to the hospital and risk exposure makes in-person consent problematic. Consent will be obtained via one of two methods: (1) obtained in-person and documented by double signature, or (2) obtained telephonically with an additional hospital signatory witness. The research team will then memorialize written consent by post (mail) or electronic mail, when possible, but telephonic consent will be sufficient for recruitment of subjects and protocol start. If the consenting party is only available via phone, the study will be discussed with this Legally Authorized Representative, and additional family member as desired, thoroughly, and the research staff will then return a call at a reasonable interval, usually in two hours, to respond to any questions. Questions provided immediately will be answered in real time. During the two hour interval, the consent form will be faxed or emailed to the legally authorized representative for review. This telephonic consent will be witnessed by another member of the hospital team to ensure that the study is clear to the family member and all questions have been answered. We will then randomize the patient and begin treatment. If and when the subject has regained the mental capacity to participate in the informed consent process, s/he will be approached by the research staff and consented clarified. If the patient does not continue consent, they will be withdrawn from the study.

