The study personnel will report adverse events as soon as they become aware of them and within 24 hours of them being informed. All adverse events or unanticipated problems will be reported to the IRB. If the adverse event is thought to be related to the intervention, the medication will be stopped and the patient will be withdrawn from the study. They will be monitored closely for resolution of the adverse event. In order to ensure that the patient receives the ideal treatment for their adverse reaction and their newly-discovered allergy is documented appropriately, the research staff will un-blind the ICU staff and themselves. This will be accomplished by keeping duplicate sealed randomization envelopes. In the case of an adverse event, the research staff will open this additional envelope and inform the treating physicians.

Side Effects

Possible side effects for patients receiving IV vitamin C include diarrhea, nausea, vomiting, heartburn, headache, insomnia, and nephrolithiasis. Possible side effects for patients receiving IV vitamin B₁ include nausea, hives, wheezing, or angioedema. In the event of these reactions, the patients will be treated immediately for their allergic reaction by the primary team and will be withdrawn from the trial as previously mentioned.

Study Withdrawal

All patients who have a serious adverse event thought to be directly related to the intervention will be withdrawn from the study. The patient or their consenting proxy may revoke consent and withdraw from the study at any point as participation is completely voluntary.

Statistical Issues

The intervention arm (vitamin B₁ and C) and the control arm (sodium chloride 0.9%) will be compared statistically for demographics and patient characteristics; including age, gender, comorbidities, need for operative intervention, enteral nutrition, and Body Mass Index (BMI). Outcomes between these two groups will also be compared including hours of vasopressor use, ventilator days, HLOS, ICU LOS, comorbidities, renal function measured by patients' GFR and creatinine levels, procalcitonin levels, SOFA scores, discharge destination, readmission rates, and mortality rates. We will do a subgroup analysis of patients with septic shock as compared to those with severe sepsis. We will also do a subgroup analysis of the patients who receive hydrocortisone as opposed to those who do not.

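### Stopping study drug for a related adverse event also takes the patient out of the study, and no all-randomised mortality analysis or vital-status follow-up is stated to offset this

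*Combined protocol and SAP*

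**What the plan says.** **Adverse events.** Under Reporting of Adverse Events, a related event has two consequences in one step: "the medication will be stopped and the patient will be withdrawn from the study". What follows is limited to the event itself: "They will be monitored closely for resolution of the adverse event". Side Effects says that patients with the reactions it lists "will be withdrawn from the trial as previously mentioned". Study Withdrawal is worded more narrowly: "All patients who have a serious adverse event thought to be directly related to the intervention will be withdrawn from the study".

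**Consent.** Under Enrollment/Randomization, patients enrolled through a representative are approached again once they regain capacity: "If the patient does not continue consent, they will be withdrawn from the study". Study Withdrawal adds that "The patient or their consenting proxy may revoke consent and withdraw from the study at any point".

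**Outcome and analysis.** The primary hypothesis concerns mortality, with no time point. Statistical Issues compares the two arms on mortality by Fisher's exact test. It defines no analysis set and does not mention withdrawn patients. Study Workflow provides 30 days of follow-up after discharge, for readmissions.

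**Planning figures.** Enrollment/Randomization gives 60 patients per arm and mortality of 35% against 30%. It gives no withdrawal rate or allowance.

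**The concern.** Stopping a study drug and leaving a study are different events. A patient whose infusion is stopped can still be followed to death or survival and counted in the assigned arm. The protocol joins the two and then describes follow-up only to resolution of the event. An analyst who wants to include such a patient has no stated source for vital status once the patient is withdrawn, and no rule requiring inclusion.

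Both kinds of exit occur after randomisation and can be linked to outcome. Withdrawal for a related event depends on what happened during treatment. Refusal to continue consent is open only to patients who are alive and have regained capacity, although some may die later. If those lost differ in mortality from those kept, and the pattern is not the same in both arms, the remaining groups are no longer the randomised ones. The protocol's stated reason for randomising is to remove selection bias, and this gap could let some of it back into the primary comparison.

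**Working it through.** **Inputs from the protocol (Enrollment/Randomization).** 60 per arm; control mortality 35%, so 0.35 × 60 = 21 deaths; active mortality 30%, so 0.30 × 60 = 18 deaths. All numbers lost, and the mortality of those lost, are assumptions.

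**Baseline, nobody lost.**
- Difference: 21/60 − 18/60 = 35.0% − 30.0% = 5.0 points.
- Standard error: √(0.35 × 0.65/60 + 0.30 × 0.70/60) = √(0.4375/60) = 8.5 points.
- Fisher's exact p = 0.70.

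**Losses in the active arm only.** If *w* patients with mortality *m* drop out of the comparison, the difference seen, in points, is

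35 − 100 × (18 − *m* × *w*)/(60 − *w*)

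| Lost (*w*) | *m* = 10% | *m* = 30% | *m* = 50% |
|---|---|---|---|
| 2 | 4.3 | 5.0 | 5.7 |
| 4 | 3.6 | 5.0 | 6.4 |
| 6 | 2.8 | 5.0 | 7.2 |

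For example, *w* = 6 and *m* = 50% gives 35 − 100 × (18 − 3)/54 = 35 − 27.8 = 7.2. Losses at the arm's own mortality (middle column) cause no distortion. In the outer columns the shift is at most 2.2 points, about a quarter of the standard error (2.2/8.5 = 0.26).

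**Outer limits for the same losses.**

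| Lost (*w*) | All would survive | All would die |
|---|---|---|
| 2 | 18/58: 4.0 points, p = 0.70 | 16/58: 7.4 points, p = 0.43 |
| 4 | 18/56: 2.9 points, p = 0.84 | 14/56: 10.0 points, p = 0.31 |
| 6 | 18/54: 1.7 points, p = 1.00 | 12/54: 12.8 points, p = 0.15 |

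The right-hand column is improbable. At 30% mortality and independence, the chance that all those lost would die is 0.3² = 9%, 0.3⁴ = 0.8% and 0.3⁶ = 0.07%.

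**Consent not continued.** Survivors number 39 (control) and 42 (active). Assume that all refusers survive.
- 10% refuse in each arm: 21/56.1 − 18/55.8 = 37.4% − 32.3% = 5.2 points. Both rates rise, but the difference barely moves.
- 10% control, 5% active: 21/56.1 − 18/57.9 = 6.3 points.
- 5% control, 10% active: 21/58.05 − 18/55.8 = 3.9 points.

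**Unknown vital status with all 60 kept in the denominator.** Each unknown moves an arm's rate by up to 1/60 = 1.7 points. Three unknowns in one arm give best-case to worst-case bounds 3/60 = 5.0 points wide, equal to the whole planned difference. Part of this sensitivity comes from the planned difference being only three deaths (21 against 18), which is a separate matter.

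**The case against.** The strongest reply is that no rule drops anyone. The arms are defined by allocation, 60 and 60, and Statistical Issues compares them without restriction. A reader might infer that withdrawn patients are excluded; the text does not say so. This stands: exclusion is a risk left open, not a stated rule.

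A reader might also infer that losses must be heavier in the active arm, because the listed reactions are attributed to the vitamins. The documents do not establish that. Treating physicians, research team and patients are blinded, and vitamins are ordered in the record for everyone, so a saline patient's symptoms could equally be judged related. Blinding limits differential loss. It does not exclude it, since true reactions may be commoner on active drug.

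Nor should the envelope sentence, "In the case of an adverse event, the research staff will open this additional envelope and inform the treating physicians", be read as showing that relatedness is judged after unblinding. The section most naturally runs in the other order: judged related, drug stopped, patient withdrawn, then unblinded.

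Two further points reduce the likely size. Most patients are expected to be intubated and sedated at diagnosis, so some milder items in "Possible side effects for patients receiving IV vitamin C include diarrhea, nausea, vomiting, heartburn, headache, insomnia, and nephrolithiasis" may often go unrecorded, and Study Workflow says that earlier human studies saw no serious side effects. Discharge destination and hospital stay are compared between arms, so in-hospital deaths may be captured anyway. Both are fair, but neither is a stated arrangement for withdrawn patients.

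Finally, consent pages were not available for review and may cover use of data after withdrawal. They could supply permission; the analysis set still has to be stated in the plan.

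**Conclusion.** The point holds as a gap with a specific cause. The protocol ties stopping study drug to leaving the study, and neither an all-randomised analysis, nor vital-status follow-up after withdrawal, nor a mortality time point is stated to offset that. Followed as written, it can remove randomised patients from the primary mortality comparison and bias the estimate.

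Size and direction are unknown. On assumed active-arm losses of up to 6, with mortality of 10% or 50% among those lost, 5.0 points becomes 2.8 to 7.2. Equal refusal of consent in both arms changes little, and nothing in the documents gives a reason for refusal to differ by arm. A reader might infer that the trial's test result is at stake. The figures do not support that: the lowest p-value in any scenario tested is 0.15, and even the extreme shift of 12.8 − 5.0 = 7.8 points is below one standard error. The issue is the validity of the estimate.

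The three statements on adverse-event withdrawal differ in scope (any related event; the listed reactions; serious, directly related events). They can all be followed at once, so this calls for clarification and does not carry the finding.

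**What to change.** 1. Reword Reporting of Adverse Events, Side Effects and Study Withdrawal so that stopping study drug does not end study follow-up. Which events stop the drug is for the investigators, who should also clarify how the three statements fit together.
2. State in Statistical Issues that all randomised patients are analysed in their assigned arm.
3. Name one fixed time point for mortality and record vital status then for every randomised patient. The existing 30-day follow-up runs from discharge, so it is not itself a common time point.
4. Where consent is not continued or is revoked, ask separately for permission to keep data already collected and to record vital status.
5. Report withdrawals by arm and reason, with a simple best-case and worst-case analysis for unknown mortality, in both directions.

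The cost is a wording change, one additional data item and possibly a line in the consent form. No extra patients are needed. The method of the existing follow-up is not described, so the effort of recording deaths cannot be judged exactly. Some loss from full revocation of consent will remain.

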Prior to the recruitment process the pharmacy will enter numbers 1-120 in ascending order into a randomizing website. This randomly assigned each number to either placebo or intervention. Prior to recruitment, kits in blocks of 10, containing either the placebo or unmixed forms of vitamin B₁ and C are made and placed in identical packages labeled with their corresponding number. These numbers will be assigned in ascending order corresponding to the order in which they are consented. Once ordered by the providers the pharmacy will open the identical kits and, if it is the intervention, mix the vitamin B₁ and C for IV administration. This process will ensure the study coordinators, healthcare providers, and the patients remain blinded. Vitamins B₁ and C will be ordered for all patients in Epic, giving the impression that all of those

enrolled are in the intervention group. However half the kits will contain the intervention and half will contain the placebo. This is being done due to logistical issues with preparing and storing the vitamin B₁ and C. Having premade kits allows the pharmacy to more easily prepare and distribute the vitamin B₁ and C. These also need to be refrigerated and given limited space kits will be made in blocks of 10 to limit crucial storage space the pharmacy needs for other medications.

We plan to enroll 120 patients; 60 in the control arm and 60 in the intervention arm. Our current mortality rate is 35% at Saint Francis Hospital and Medical Center for patients with severe sepsis and septic shock. We expect our mortality rate to decrease to 30% with this intervention. We believe this is a reasonable expectation given that Marik et al. demonstrated that his intervention group's mortality rate dropped from 40.4% to 8.5% after a similar intervention.¹⁰ In order to demonstrate this difference, 120 patients are needed according to our power calculation.

Informed Consent/Ethical Issues

We anticipate a full board IRB approval, as this is a prospective study involving vitamins B₁ and C as the intervention. Appropriate patients will be approached and consented (often via proxy consent) by members of the research team. Patients will then be randomized by computer to receive vitamin C and vitamin B₁, or normal saline (control). The treating physicians, the research team, and the patients will all be blinded. The pharmacist mixing the drugs will be the only non-blinded team member.

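### The adverse-event code-break unblinds the research staff as well as the treating team, which conflicts with the stated blinding and is not needed for its stated purpose

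*Combined protocol and SAP*

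**What the plan says.** Two parts of the combined protocol and SAP describe who knows the allocation.

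**The default state.** Enrollment/Randomization describes numbered, identical kits opened by the pharmacy and says that this keeps study coordinators, providers and patients blinded. Informed Consent/Ethical Issues adds the research team to the blinded groups and closes the list: "The pharmacist mixing the drugs will be the only non-blinded team member". Neither section mentions emergency unblinding.

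**After an adverse event.** Reporting of Adverse Events begins with a conditional rule on withdrawal from the trial: "If the adverse event is thought to be related to the intervention, the medication will be stopped and the patient will be withdrawn from the". It then gives a purpose, "In order to ensure that the patient receives the ideal treatment for their adverse reaction and their newly-discovered allergy is documented appropriately", and an action, "the research staff will un-blind the ICU staff and themselves". The mechanism follows: "This will be accomplished by keeping duplicate sealed randomization envelopes". The paragraph ends: "In the case of an adverse event, the research staff will open this additional envelope and inform the treating physicians".

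On roles, the plan says that investigators manage the data and that study personnel report adverse events. It does not name who judges relatedness, who records outcomes, or who stores the envelopes.

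**The concern.** A code-break should give the allocation to those who need it for the patient's care and to nobody else. Here the people running the study also learn it, although the plan gives no task for which they need it.

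What is at stake is the handling of an unblinded patient from that point on: judging later events, revising an earlier relatedness judgement, watching for resolution of the event, and collecting whatever follow-up continues, such as SOFA scores, discharge destination or 30-day readmission. A second problem is that the closing sentence, taken by itself, lets any adverse event open the envelope. Staff could then know the arm before they decide whether the event was due to the study drug, and that decision leads to withdrawal.

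**Working it through.** The plan gives no figure on this point to reproduce, so the check sets the statements side by side.

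1. **Who is blinded.** Informed Consent/Ethical Issues makes the pharmacist the sole exception. Reporting of Adverse Events adds two groups, the ICU staff and the research staff. For the ICU staff this is a normal safety exception that the blinding statement omits. For the research staff it is a conflict.

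2. **Does the purpose require it?** Two reasons are given: treatment of the reaction and documentation of the allergy. The Side Effects section assigns treatment to the primary team. The plan does not link either reason to a research task. The pharmacist already holds the allocation, so the treating physician can be told without passing it through the research staff.

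3. **Which events open the envelope?** The paragraph opens with events attributed to the intervention. Its purpose sentence speaks of a reaction and an allergy. Its last sentence, "In the case of an adverse event, the research staff will open this additional envelope", carries no condition on relatedness or seriousness. Two nearby sections add further wording on withdrawal, though not on envelopes. Side Effects withdraws patients who have any of the listed reactions, and Study Withdrawal refers to serious events directly attributed to the intervention. The plan does not say which of these governs.

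4. **What is known when relatedness is judged?** The answer depends on step 3.
   - If the opening condition governs, the order is relatedness judgement, then stopping and withdrawal, then unblinding. The first judgement for that patient is made blind.
   - If the closing sentence governs, the envelope may be opened first and the judgement is exposed.

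5. **What remains exposed under either reading?** Later judgements and follow-up data for the same patient. How much data this involves is unknown, because the plan does not say whether outcomes are collected after withdrawal.

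6. **How many patients?** The documents give no adverse event rate. As an assumption only, let a share *r* of the 120 planned patients trigger a code-break; the number unblinded to research staff is 120 × *r*:
   - *r* = 2%: 120 × 0.02 = 2.4, about 2 patients
   - *r* = 10%: 120 × 0.10 = 12 patients
   - *r* = 30%: 120 × 0.30 = 36 patients

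   The range is wide because the trigger is unsettled. It counts unblinded patients and does not measure bias.

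**The case against.** The strongest defence is that the two sections describe different things: one the normal state produced by the kit process, the other a safety exception for a single patient. This holds in full for the ICU staff. It does not explain why the research staff are included.

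The second defence is that, in the paragraph's natural order, relatedness and withdrawal are settled before the envelope is opened. This also stands, and it limits the concern on that reading to what happens afterwards. It does not remove the unconditional last sentence.

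Third, the primary hypothesis concerns mortality, and many other outcomes are durations, counts or laboratory values. These leave little room for an assessor's expectations, so the likely effect on the main result is small.

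A reader might infer more than the documents support in three ways:

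- **That the unblinded staff are the people who record outcomes and judge relatedness.** This is plausible, but no such roles are assigned. The supportable statement is that nothing in the plan keeps these tasks with blinded people.
- **That deaths would open many envelopes.** At the plan's mortality rates, 0.35 × 60 + 0.30 × 60 = 21 + 18 = 39 of 120 patients. The arithmetic is right but the use is not. The plan does not say that a death opens an envelope, the stated purpose of treating a reaction and recording an allergy does not fit a patient who has died, and unblinding at death cannot influence that patient's withdrawal, later SOFA scores or readmission.
- **That research staff hold the envelopes.** The plan says that they open them and is silent on storage.

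**Conclusion.** The point holds for the research staff. Their self-unblinding conflicts with the blinding statement and serves no purpose that the plan gives. The conflict and the inconsistent trigger are both on the page and need no assumption.

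The consequence is more modest and partly conditional. Later event judgements and follow-up data for unblinded patients can be affected, provided that research staff perform those tasks and that data collection continues after withdrawal; the plan settles neither. Initial relatedness judgements are exposed only if the unconditional sentence is followed. The number of patients affected cannot be derived from the documents, and any effect on mortality is likely small. The change is still worth making because it removes an avoidable source of bias at little cost.

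**What to change.** 1. In Reporting of Adverse Events, delete the words that extend the unblinding to the research staff.
2. Replace the envelope step so that the already unblinded pharmacist gives the allocation directly to the treating physician. State that research staff, and anyone who assesses relatedness or records outcomes, remain blinded, and name who holds those roles.
3. Log each code-break: patient, date, reason and who was told.
4. Reconcile the sentences in Reporting of Adverse Events on which events open the envelope, and check them against Side Effects and Study Withdrawal. Which events qualify is for the investigators to decide; the text should state one rule.
5. Add the emergency exception to the blinding statement in Informed Consent/Ethical Issues.

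The cost is a protocol amendment and a changed route for the code. The treating physician receives the same information. The one practical drawback is that pharmacy must be reachable whenever unblinding is needed; the documents do not describe its hours, so this should be confirmed before the change is adopted.

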The objective of this study is to determine if the administration of IV vitamins B₁ and C are effective in decreasing the mortality rates of patients with severe sepsis or septic shock. In addition, we will investigate if there are benefits to those patients who also receive hydrocortisone in an effort to explore the synergistic relationship that vitamins B₁ and C have with hydrocortisone.

Overview of Study Design

Patient Selection Criteria

1. Inclusion Criteria: Patients admitted to the ICU at Saint Francis Hospital and Medical Center who are:
 - a. Between the ages of 18 and 90 years old
 - b. Have severe sepsis or septic shock
 - i. Severe sepsis and septic shock will be defined by the Surviving Sepsis 2012 guidelines¹¹
 - c. Weight more than 30 kg
 - d. Full code
2. Exclusion Criteria: Patients
 - a. Not diagnosed with severe sepsis or septic shock
 - b. Younger than 18 or older than 90 years old
 - c. Who are pregnant
 - d. Weigh less than 30 kg

- e. Currently on hemodialysis
- f. Not located in the ICU
- g. Do not resuscitate (DNR) or do not intubate (DNI), no escalation of care, or comfort measures only (CMO)

Enrollment/Randomization

Once identified, patients who meet inclusion criteria will be approached. The majority of patients are likely to be intubated and sedated at the time of their diagnosis of severe sepsis or septic shock. In these cases, the next of kin or consenting party will be approached for each patient. The providers in the ICU, mainly physician's assistants (PAs) and residents, always contact patient's family members for consent for central lines and other invasive procedures while in the ICU. The study staff will speak to this same consenting person (in person or on the phone) and will ask them about the potential enrollment of their loved one in the study. In the absence of documentation of a healthcare proxy or conservator (as is often the case with septic patients, as it is an unexpected illness), priority will be given to the patient's spouse, followed by an adult child, followed by a parent, followed by an adult sibling. .

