Data will be kept on an encrypted, password-protected computer behind two locked doors. Data will be managed by the investigators who will each have their own login.

Study Workflow

Patients admitted to the ICU who have severe sepsis or septic shock will be identified by the nursing staff, PAs, or physicians caring for them. These patients' consenting party will be approached within 24 hours of their presentation to the ED in an attempt to obtain informed consent. Following consent, the pharmacy will be notified of the study patient, randomization will occur, and the mixed medications (control or intervention) will be delivered to the patient's bedside in the ICU. Consented patients will receive 1.5g of vitamin C in 100mL of 0.9% sodium chloride (normal saline) every six hours for four days or until discharge from the ICU, whichever happens first (seventeen dose maximum). In addition, they will receive 200 mg IV vitamin B₁ every 12 hours in 100 mL of normal saline for four days or until ICU discharge (whichever happens first, nine dose maximum). Patients in the control arm will receive the 100 mL of 0.9% sodium chloride every six hours and 100 mL of 0.9% sodium chloride every 12 hours to act as placebos for the vitamin C and B₁ respectively. Doses up to 200 mg/kg/day were found to be safe in humans in one study.⁶ Several studies have been conducted in human subjects using IV vitamin B₁ and C, often at higher doses than proposed here, and have not seen serious side effects.^{10,12-14}

Some patients may receive hydrocortisone IV for refractory septic shock outside of this study protocol. This will be at the discretion of the treating physician and will not be included in the randomized and blinded intervention. Hydrocortisone has been shown in some studies to help

in patients with refractory septic shock.^{15,16} However, it is not uniformly employed. Patients receiving hydrocortisone will undergo a subgroup analysis to better elucidate the synergistic effects of hydrocortisone with vitamins B₁ and C.

After discharge, patients will be followed for 30 days to track hospital readmissions.

Reporting of Adverse Events

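### No between-arm comparison of adverse events is specified and events are gathered only as staff learn of them; scheduled chart collection and a table by arm would be a cheap improvement

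*Combined protocol and SAP*

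**What the plan says.** The Side Effects section lists expected harms of both vitamins. Those of vitamin C "include diarrhea, nausea, vomiting, heartburn, headache, insomnia, and nephrolithiasis"; those of vitamin B1 are nausea, hives, wheezing and angioedema. That makes ten distinct events, since nausea appears twice.

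Under Reporting of Adverse Events, staff report an event within 24 hours of learning of it, and all events go to the IRB. An event judged related leads to stopping of study medication, withdrawal, monitoring to resolution and unblinding by a duplicate envelope. The section names no criteria for relatedness, assessor, grading, collection schedule or collection window.

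The between-arm outcomes are in Statistical Issues: "Outcomes between these two groups will also be compared including hours of vasopressor use, ventilator days, HLOS, ICU LOS, comorbidities, renal function measured by" GFR and creatinine, followed by procalcitonin, SOFA, discharge destination, readmission and mortality. The same section assigns Fisher's exact test to gender, operative intervention, mortality and 30-day readmission. No adverse event appears among the outcomes or the tests.

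Study Workflow gives the follow-up after discharge: "After discharge, patients will be followed for 30 days to track hospital readmissions". Enrollment/Randomization, explaining proxy consent, says: "The majority of patients are likely to be intubated and sedated at the time of their diagnosis of severe sepsis or septic shock".

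**The concern.** Diarrhea, vomiting or wheezing in an ICU patient with sepsis can have causes other than the study drug, so a relatedness call in one patient is weak evidence. The blinded saline arm is the natural reference: an excess in the vitamin arm, counted whatever anyone thought of the cause, can be attributed to treatment within the limits of chance. The plan specifies no such count.

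Collection matters as much as analysis. Reports that depend on someone noticing give an uncertain numerator, and a table added at the end cannot fully recover what was not looked for. If few reports are filed, readers may take the regimen to be well tolerated without knowing how hard anyone looked. Because the plan does not say whether data are kept for patients withdrawn after a related event, the patients most informative about harm could also leave the outcomes that are compared.

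**Working it through.** The plan gives no figure for adverse events, so there is none to reproduce on this point. The one design input used is the size: "We plan to enroll 120 patients; 60 in the control arm and 60 in the intervention arm". I take 60 per arm as given. (Whether 120 follows from 35% versus 30% mortality is a separate question. It does not at two-sided 0.05 and 80% power, which are assumed because the plan states neither: 1,377 per arm would be needed. Nothing below depends on this.)

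**1. Where each listed effect could show.**

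| Listed effect | How it is found | Named among compared outcomes or tests? |
|---|---|---|
| Nausea, heartburn, headache, insomnia | Self-report | No |
| Diarrhea, vomiting | Observed by staff | No |
| Hives, wheezing, angioedema | Observed by staff | No |
| Nephrolithiasis | Testing, or reported pain | No |

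Self-report is needed for 4 of 10, or 5 of 10 if stones are assumed to come to light only through pain. For vitamin C alone it is 4 of 7.

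**2. What the compared outcomes do cover.** Mortality, daily SOFA, creatinine, GFR, vasopressor hours, ventilator days and readmissions are compared between randomised, blinded arms. Harm acting through death, organ failure, renal function or readmission could appear there. None of them counts the ten listed effects.

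**3. What 60 patients could rule out.** If no event of a given type is seen among 60 treated patients, all of whom were checked:
- one-sided 95% upper limit: 1 − 0.05^(1/60) = 0.0487, or 4.9%
- upper limit of a two-sided 95% interval: 1 − 0.025^(1/60) = 0.0596, or 6.0%

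**4. Precision of a between-arm difference.** The documents give no event rates. Assuming 20% in both arms, the 95% half-width is 1.96 × √(2 × 0.20 × 0.80 / 60) = 1.96 × 0.0730 = 0.143, about ±14 percentage points.

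**5. What a test could detect.** Fisher's exact test, two-sided 0.05, 60 per arm, power by exact binomial enumeration. With zero events in one arm, at least 6 are needed in the other for p ≤ 0.05. For 80% power:

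| Control rate (assumed) | Treated rate needed |
|---|---|
| 1% | 16% |
| 5% | 24% |
| 10% | 32% |
| 20% | 45.5% |
| 30% | 56.5% |

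The comparison is feasible but would show only large excesses, so intervals are more useful than tests.

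**The case against.** The strongest reply is that randomised, blinded comparisons bearing on harm already exist, that the outcome list is introduced as illustrative so adverse events might still be compared, and that at this size a table would rarely be conclusive. The first part stands and limits the point to adverse events themselves. The second stands in wording: the documents specify no comparison, which is different from excluding one. But the plan assigns adverse events no test and no scheduled collection, and a late comparison of passively gathered reports would be weak. The third is true of any plan with 60 per arm, and is a reason to report intervals rather than nothing.

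A reader might infer more than the documents support:
- **That the listed effects are mostly ones sedated patients cannot report.** Four of ten need self-report. The sentence on sedation describes the time of diagnosis, not the whole of dosing or the hospital stay, and the consent section provides for patients who regain capacity.
- **That the trial has no randomised safety comparison, or cannot separate drug harm from sepsis.** Step 2 shows otherwise for death, organ function, renal function and readmission.
- **That relatedness calls are guesswork because these events are common in sepsis.** The documents give no background rates.
- **That harms after discharge are ignored.** Reporting on awareness has no stated end date, and a stone leading to readmission would be counted as a readmission. What is missing is a stated collection window and a purpose for follow-up beyond readmissions.

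**Conclusion.** The point holds as a gap in specification and in method of collection. No between-arm comparison of adverse events, serious adverse events or discontinuations is specified. Events are collected on awareness and judged one patient at a time, with no schedule or window, and the stated follow-up after discharge covers readmissions only. The outcomes that are compared do not measure the ten listed effects, and four of those may be missed while patients are sedated.

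The gain from repair is real but limited: an upper limit of 4.9% or 6.0% after zero events in 60, and about ±14 points at 20% in both arms. These figures assume full enrolment, treatment and checking of 60 patients per arm; the 20% is an assumption. This is a low-cost improvement that should be made. It does not threaten the mortality comparison.

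**What to change.** Add adverse events to the between-arm outcomes in Statistical Issues. For all patients who received any kit, tabulate by arm the number with each listed effect, any serious adverse event and any event leading to discontinuation. Count them regardless of judged relatedness and include patients withdrawn for an event. Report risk differences with exact 95% intervals.

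Collect the observable listed effects (stool and emesis charting, rash, wheeze, angioedema) from existing charts in both arms on each dosing day. Record any adverse event or kidney stone found in the records used for the 30-day readmission check.

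An envelope is opened after an adverse event, so later reports for that patient may be unblinded. State this with the table; no change to the unblinding or withdrawal rules is proposed here.

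The cost is one table and modest extra data entry. This assumes that nursing charts already hold these signs and that the readmission check uses records that can show other events; the documents do not say how that check is done. A stone treated outside those records would still be missed, symptoms needing self-report would remain under-counted during sedation, and intervals for rare events will be wide.
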